4 ANALYSIS POPULATIONS

The Primary Analysis Cohort will include all enrolled study subjects in whom an attempt to use the device is made, excluding the first two roll-in subjects treated per each Investigator. Subjects who sign the consent form but are deemed ineligible for the study prior to any attempt to use the MANTA device will not be included in the Primary Analysis Cohort or the Roll-In Cohort. Use of the MANTA puncture locating dilator at the beginning of the large-bore intervention procedure is not considered an attempt to use the MANTA device. Placement of the MANTA sheath following confirmation of intra-procedure exclusions is the start of attempted device use, and the time this sheath is removed will define the starting time of efficacy assessments.

The Primary Analysis Cohort, the Per Protocol Set, and the Safety Evaluation Set as described below will be comprised of the subjects in the Primary Analysis Cohort. Subjects in the Roll-In Cohort will be summarized separately from subjects in the Primary Analysis Cohort.

The following populations will be defined for the statistical analysis of this clinical trial:

4.1 Primary Analysis Cohort

The Primary Analysis Cohort (PAC) will consist of all non-roll-in subjects in whom an attempt to use the device was made (i.e., subjects who sign the consent form but are deemed ineligible for the study prior to any attempt to use the MANTA device will not be included in the efficacy analyses). Subjects who are excluded due to intra-procedural exclusions will be excluded from the efficacy analyses as long as the MANTA sheath has not been introduced; use of the MANTA puncture locator at the beginning of the procedure is not considered "attempted use" of the MANTA device.

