**Intra-Procedure Exclusions:**

27. Puncture site in the profunda femoris artery, superficial femoral artery, or at the bifurcation of these arteries
28. Common femoral artery suspected to have experienced a back wall puncture or underwent  $>$  one (1) arterial puncture during the catheterization procedure
29. Difficult dilation from initial femoral artery access (e.g., damaging or kinking dilators) while step dilating up to the large-bore device
30. Presence of ipsilateral femoral venous sheath
31. Puncture site located above the most inferior border of the epigastric artery (IEA) and/or above the inguinal ligament based upon bony landmarks
32. Marked tortuosity of femoral or iliac artery
33. Patient did not receive any antiplatelet or anticoagulant medications before or during the endovascular interventional procedure
34. ACT  $>$ 250 seconds prior to removal of the sheath or interventional device
35. Systolic blood pressure  $>$ 180 mmHg or diastolic blood pressure  $>$ 110 mm Hg, unless systolic or diastolic pressure can be lowered by pharmacological agents prior to closure
36. Antegrade puncture during the index procedure
37. Interventional sheath or device in place  $>$ 6 hours
38. Possible bacterial contamination of the procedure sheath or surrounding tissues during the procedure
39. Intra-procedural complication(s) at the femoral access site pre-sheath removal including: 1. Bleeding or swelling around the large bore sheath that may indicate hematoma formation and/or pseudoaneurysm formation; and 2. Peri-procedural angiographic evidence of thrombus formation or significant injury in the aorta or iliac vessels associated with procedural large bore sheath placement and/or sub-optimal anticoagulation
40. Systolic blood pressure  $<$ 90 mm Hg just prior to planned vascular closure
41. Procedure sheath or interventional device  $>$ 25F outer diameter required during the procedure

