## **7.4. Screening and Interventional Procedure Data**

The following tests and other selected assessments will be performed during the index interventional procedure prior to attempted MANTA deployment to confirm that the patient does not meet any of the intra-procedure exclusions (see Section 6.5.3):

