### **9.3. Relationship of Adverse Event to Device/Procedure**

Each reported AE will be assessed by the Investigator for its primary suspected relationship to the closure device or to the interventional procedure.

- MANTA Study AEs related to the interventional procedure (e.g., TAVI, EVAR procedure) or closure of a non-target access site are considered Procedure-Related AEs.
- MANTA Study AEs related to the MANTA closure device and/or its deployment (in total, the closure procedure) are considered Device-Related AEs.
- MANTA Study AEs that are related to neither the interventional procedure nor the MANTA device are considered NOT related to the device or procedure.

The causal relationship of an AE to the device or procedure will be classified as follows:

- Not Related: An AE which cannot be attributed to the study device or initial study procedure.
- Unknown Relationship: The relationship of the AE to the device or procedure cannot be determined.
- Possible: The clinical event occurs within a reasonable time sequence to study procedure/study device and there is some evidence to “possibly” suggest a causal relationship. However, the influence of other factors such as underlying disease, concomitant medications, or concurrent treatment may have contributed to the event.
- Probable: The temporal sequence between the device use or procedures and the event is such that the relationship is likely or subject’s condition or concomitant therapy could have caused the AE.
- Definite: The clinical event occurs in a plausible time relationship to study procedure/study device and cannot be explained by any concurrent disease or other devices, drugs or chemicals.

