4.3 Safety Evaluation Set

The Safety Evaluation Set (SES) will consist of all non-roll-in subjects in whom an attempt to use the MANTA device was made. (i.e., subjects who sign the consent form but are deemed ineligible for the study prior to any attempt to use the MANTA device will not be included in the safety analyses). Subjects who are excluded due to intra-procedural exclusions will be excluded from the safety analyses as long as the MANTA sheath has not been introduced; use of the MANTA puncture locator at the beginning of the procedure is not considered "attempted use" of the MANTA device. The Safety population will be used for the analysis of safety endpoints as well as procedural and discharge data.

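### SAP 4.1 and 4.3 can drop a subject after a failed MANTA sheath insertion if a listed intra-procedure exclusion is recognised only then; attempted use should begin at the first insertion attempt

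*SAP*

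**What the plan says.** SAP 4.1 defines the Primary Analysis Cohort (PAC) as "all non-roll-in subjects in whom an attempt to use the device was made". SAP 4.3 defines the Safety Evaluation Set (SES) in the same way. Each section then adds a removal rule for subjects with an intra-procedural exclusion. In 4.1 they "will be excluded from the efficacy analyses as long as the MANTA sheath has not been introduced"; in 4.3 they "will be excluded from the safety analyses as long as the MANTA sheath has not been introduced". Both sections state that early use of the puncture locator does not count as attempted use.

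The introduction to SAP 4 fixes the start of attempted use: "Placement of the MANTA sheath following confirmation of intra-procedure exclusions is the start of attempted device use". Neither placement nor introduction is defined for a partial or failed insertion.

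Protocol 7.4 says the eligibility checks are "performed during the index interventional procedure prior to attempted MANTA deployment to confirm that the patient does not meet any of the intra-procedure exclusions". The intra-procedure exclusions are items 27 to 41 of Protocol 6.5.3. Some carry their own time limit: item 29 covers difficult dilation "while step dilating up to the large-bore device", and item 39 begins "Intra-procedural complication(s) at the femoral access site pre-sheath removal including". Items 28 (suspected back-wall puncture) and 32 (marked tortuosity) carry no cut-off tied to sheath removal. Item 40 (systolic pressure below 90 mm Hg) runs up to just before closure.

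Protocol 6.5.5 adds a third boundary. A subject whom the investigator exits before the device is implanted leaves with no data collected except the reason.

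**The concern.** The inclusion rule turns on an attempt; the removal rule turns on the sheath having gone in. The two agree unless an insertion is attempted and does not succeed. For such a subject, if a listed exclusion is then recognised, the plan gives two answers, and the more specific sentence points to removal.

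The same clause governs both co-primary analyses. The trial is single-arm and unblinded (SAP 2.2.2) and is judged against fixed goals. A rule under which membership may be settled after the first device step has gone badly is therefore outcome-dependent selection, and it can act only in the device's favour on safety.

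The omission would also sit badly with the rest of the protocol. On relatedness, Protocol 9.3 says "MANTA Study AEs related to the MANTA closure device and/or its deployment (in total, the closure procedure) are considered Device-Related AEs". Protocol 9.5.1 makes serious events reportable from attempted placement onward, and 9.6 records as device deficiencies those devices with an insertion attempt that did not stay in the subject. Such a subject could have a device deficiency and a reportable serious event on file and still be absent from the SES.

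**Working it through.** **1. The plan's own sample sizes.** Inputs (Protocol 8.2, SAP 3): assumed Major Complication rate 13%, goal 19.9%, one-sided 0.025, n = 250, stated power 80%. The criterion is an exact upper 97.5% bound below 19.9%. With x events in n subjects, that bound is the 0.975 quantile of Beta(x+1, n−x).

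- 37/250: bound 19.82%, pass. 38/250: bound 20.26%, fail. The rule at n = 250 is therefore at most 37 events.
- P(X ≤ 37 | 250, 0.13) = 82.7%; P(X ≤ 37 | 250, 0.199) = 2.3%. The stated 250 reproduces, with 80% as a floor.
- Time to Hemostasis, mean 6, SD 11, goal 10: the noncentral t at n = 62 gives 80.45%. This also reproduces.

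**2. Safety: omitted subjects put back.** The documents give no number of failed insertions, so the count k is an assumption. As the worst case, every restored subject is taken to have a Major Complication, so x/n becomes (x+k)/(n+k).

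| Starting result | Restored | Result | Upper bound | Decision |
|---|---|---|---|---|
| 37/250 (boundary) | 0 | 37/250 | 19.82% | pass |
| | 1 | 38/251 | 20.18% | fail |
| 33/250 (about 13%) | 0 | 33/250 | 18.04% | pass |
| | 5 | 38/255 | 19.88% | pass |
| | 6 | 39/256 | 20.23% | fail |
| 34/263 (about 13%) | 0 | 34/263 | 17.59% | pass |
| | 6 | 40/269 | 19.69% | pass |
| | 7 | 41/270 | 20.03% | fail |

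**3. Safety: chance of passing when the true all-attempt rate is exactly 19.9%.** With 263 analysed the rule is at most 39 events (39/263: 19.71%; 40/263: 20.13%). If a fraction d of attempts is dropped and a share f of those had events, the rate among those kept is (0.199 − d·f)/(1 − d), and the chance of passing is P(X ≤ 39 | 263, that rate).

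| Dropped, d | f = 100% | f = 25% |
|---|---|---|
| 0% | 2.1% | 2.1% |
| 1% | 4.3% | 2.2% |
| 2% | 8.4% | 2.3% |
| 3% | 15.2% | 2.4% |

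Both d and f are assumptions. The size of the effect depends almost wholly on f.

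**4. Time to Hemostasis.** Start from 250 subjects with mean 6 and SD 11: bound 6 + t(0.975, 249) × 11/√250 = 7.37 min. Add k subjects at T minutes each and recompute the mean, SD and bound:

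- k = 5 at 37.17 min (the longest time in the EU study, Protocol 1.4): 8.06.
- k = 20 at 37.17 min: 9.91.
- k = 10 at 60 min: 9.91.
- k = 5 at 120 min: 10.61, fail.

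The T values are assumptions. The clock starts when the MANTA sheath is withdrawn (Protocol 7.6, SAP 4). If the sheath never entered, there is no start time and the value would be imputed. SAP 5.1 uses the worst value at the same site. Protocol 8.3.3 uses the longest time of any subject when surgical repair prevents evaluation.

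**The case against.** The strongest reply is that the sections can be read together. A failed insertion is an attempt in plain language, so 4.1 and 4.3 include it. SAP 4 puts sheath placement after the exclusions are confirmed. The removal clause reaches only subjects who meet a listed item, and a failed MANTA sheath insertion is not listed. Citing tortuosity after a failed insertion would misuse a criterion meant to be checked earlier. Screen-failure reasons are recorded (Protocol 6.5.5) and intra-procedure screen failures are counted by site (SAP 6.1.1).

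Most of this stands, and it rules out two stronger readings that a reader might infer.

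- **That the SAP lets a failed insertion as such be reclassified as a screen failure.** It does not; a listed exclusion must also be met.
- **That the SAP moved the exclusion cut-off later than the protocol.** Items 34 and 39 are tied to removal of the procedure sheath, but Protocol 7.4 allows checks up to attempted deployment, item 40 runs to just before closure, and 6.5.5 uses implantation, which is later than sheath introduction.

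Two further points also stand. Major Complications i to iv must be attributable to MANTA or its performance, so a subject whose MANTA sheath never entered need not count as an event. And no document gives a failed-insertion rate.

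The reply does not remove the conflict between the two sentences. Nothing requires the exclusion decision to be timed, and nothing bars one made after a failed attempt. A recorded reason and a site count would not show whether the decision came before or after that attempt.

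**Conclusion.** The point holds as a narrow gap in the definition of both primary sets: a subject with a failed insertion attempt and a late-recognised exclusion is included by one sentence and removed by the next. Its frequency cannot be estimated from the documents.

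The consequence lies mainly with safety, and near the boundary. One omitted event is enough at 37/250. About the planned rate, six (from 33/250) or seven (from 34/263) are needed, all with events. A reader might take the 15.2% chance of passing as the expected inflation. It requires 3% of attempts to be dropped, every one with a Major Complication, and a true rate exactly at the goal; with events in a quarter of those dropped, the figure is 2.4% against 2.1%.

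A material bias in mean Time to Hemostasis is not shown. The bound stays below 10 minutes in most of the cases tried, and the value for a sheath that never entered would depend on imputation.

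The change is still worth making before database lock, because it is cheap and removes a selection step that could depend on outcome.

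**What to change.** In SAP 4, 4.1 and 4.3, replace the introduction-based clause with wording such as:

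> The first attempt to insert the MANTA sheath, successful or not, is attempted use and places a non-roll-in subject in the PAC and the SES. An exclusion identified after that point is a protocol deviation, not a screen failure.

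Then:

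- Record the time of the exclusion decision on the eCRF, so that its order relative to the first insertion attempt can be checked.
- Reconcile Protocol 6.5.5, which lets a subject exit before implantation without data collection, with this attempt-based rule.
- Leave the protocol's timing of the exclusions relative to procedure-sheath removal as it is. A subject excluded before any insertion attempt remains a screen failure.

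The cost is SAP wording, one time field and an alignment of Protocol 6.5.5. The planned sample size does not change. The small downside is that a few failed insertions will count against the device.

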4.2 Per Protocol Set

The Per Protocol Set (PPS) is the subset of subjects in the PAC for whom all assessments planned in the protocol were performed with no major protocol deviations. Major protocol deviations will include:

1. Informed Consent procedure violations
2. Inclusion/Exclusion violations
3. Missing/out-of-window by >12 month baseline CTA
4. Missing Time to Hemostasis
5. Missing 30-day visit

Subjects found to have major protocol deviations will be excluded from the PPS. The Per Protocol analysis of the primary and secondary effectiveness endpoints and primary safety endpoints will be used for supportive analysis.

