## Schedule of Assessments

Assessment/ Interval	Screening	Index Proce- dure	Pre- MANTA Closure Procedure	MANTA Closure Procedure	Post- MANTA Closure Procedure	Hospital Discharge	30D & 60D Follow-Up 
Subject Eligibility/Informed Consent	X						
Clinical Exam	X						X
Medical History	X						
Medication Use	X					X	X
Laboratory Tests	X 						
Pregnancy Test	X 						
CT Angiographic Scan	X 						
ABI (Ankle Brachial Index)	X				X	X	X
Duplex U/S						X 	X 
Femoral Angiography		X 			X 		
Activated Clotting Time (ACT)			X				
Target Femoral Access Site External Visual Assessment			X		X	X	X
Time to Hemostasis					X		
Time to Ambulation						X	
Adverse Events		X	X	X	X	X	X

1. Female subjects of child bearing potential only. Test to be conducted within 7 days of planned Index procedure or according to standard of care for percutaneous interventional procedures requiring contrast and angiography. Urine pregnancy test is acceptable.
2. After gaining femoral artery access and prior to large-bore sheath placement, perform target (ipsilateral) common femoral angiography to rule out intra-procedure exclusion criteria.
3. Within approximately 10 minutes post-MANTA deployment, perform target (ipsilateral) common femoral angiography from contralateral access site to evaluate patency into the ipsilateral common femoral artery.
4. 30 day follow-up window is  $\pm 7$  days; 60 day follow-up window is  $\pm 14$  days.
5. Duplex ultrasound should be performed at 60-day visit if there are abnormal ultrasound findings at 30-day visit.
6. Ultrasound must be performed no later than 48 hours post-MANTA deployment, if discharge is delayed. In addition, any suspected hematoma, pseudoaneurysm or AV fistula at the MANTA site should be confirmed with ultrasound.
7. Within 7 days of planned index procedure or according to standard of care for percutaneous interventional procedures requiring contrast and angiography.
8. Within 180 days prior to subject informed consent.

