## 8 Statistical Methods

### 8.1. Study Hypotheses

#### 8.1.1 Effectiveness

The primary and secondary effectiveness analyses will be performed on both the Primary Analysis dataset (all Analysis Cohort subjects with an attempt to treat and having an assessment of the primary effectiveness parameter) and the Per-Protocol dataset (subjects from the Intent-to-Treat dataset with no major protocol violations). Results based on the Primary Analysis and the Per-Protocol datasets will be presented in the clinical report. Differences between the results will be examined. All primary and secondary effectiveness parameters will be analyzed. Roll-in subjects will be analyzed separately from the Analysis Cohort.

The primary effectiveness hypothesis is that mean Time to Hemostasis is less than the Performance Goal of 10 minutes, as follows:

$H_0: \mu \geq 10$   
vs.  
 $H_A: \mu < 10,$

where  $\mu$  is the population mean Time to Hemostasis.

The secondary endpoints are as follows:

1. Technical Success
2. Ambulation Success
3. Time to Ambulation
4. Treatment Success
5. Procedure Time

Technical Success, Ambulation Success, Time to Ambulation, Treatment Success and Procedure Time will be analyzed and reported but there will be no formal statistical test on these endpoints.

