6.1.2 Protocol Deviations

The deviations occurring during the clinical trial will be determined to be major or minor by the Sponsor and data management group prior to database lock and will be summarized descriptively. A by-subject listing of all deviations will also be prepared. Categories of protocol deviations include:

- Informed Consent Procedure
- Inclusion/Exclusion
- Concomitant Medication/Therapy
- Laboratory Assessments/Procedures
- Study Procedures
- SAE Reporting/UADE Reporting
- Visit Schedule/Interval
- Other

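### SAP 4.2 gives two incompatible membership rules for the supportive Per Protocol Set, and two of its listed exclusions can remove subjects because of a bad outcome

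*SAP*

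**What the plan says.** SAP 4.2 takes the Per Protocol Set (PPS) from the Primary Analysis Cohort (PAC) and describes it as subjects "for whom all assessments planned in the protocol were performed with no major protocol deviations". It continues with "Major protocol deviations will include" and lists five items: consent violations, eligibility violations, a CTA item worded "Missing/out-of-window by >12 month baseline CTA", missing Time to Hemostasis, and a missing 30-day visit. The sentence that carries out the exclusion reads "Subjects found to have major protocol deviations will be excluded from the PPS". It does not repeat the condition about assessments.

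SAP 6.1.2 says that deviations "will be determined to be major or minor by the Sponsor and data management group prior to database lock". It does not refer to the list in 4.2.

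Protocol 8.1.1 defines its Per-Protocol dataset as "subjects from the Intent-to-Treat dataset with no major protocol violations". It gives no list and no condition on completed assessments, and neither document defines an Intent-to-Treat dataset. The same section commits to presenting effectiveness in both datasets and examining the differences. SAP 4.2 calls the per-protocol analyses supportive and applies them to the effectiveness endpoints and primary safety. SAP section 8 records no change from the planned analyses.

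**The concern.** Two programmers working from SAP 4.2 could build different sets, each with a sentence of the plan behind it. The all-assessments rule removes subjects for things that happen after treatment: a missed ABI, a missed duplex scan, a missed 60-day visit, or death before 60 days. None of these bears on whether the closure was done according to protocol.

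The list has a second weakness. Items 4 and 5 depend on data that can be missing because the device failed or the subject did badly. Removing such subjects lowers both the mean Time to Hemostasis and the Major Complication rate in the PPS, so the supportive result would lean towards the device. The trial is single-arm and unblinded, and Time to Hemostasis is known on the day of the procedure. An open list would therefore be completed by people who can see the results.

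At stake is the value of the PPS as a check on the main analysis, together with the subject characteristics and procedural data that SAP 2.8.1 and 2.8.2 also summarise in this set.

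**Working it through.** The plan states no size for the PPS, so there is no figure to reproduce. The check sets the rules side by side and then illustrates the size.

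**1. The two rules applied to the same subject**

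| Subject | All-assessments rule | Major-deviation list |
|---|---|---|
| Misses only the 60-day ABI (required by Protocol 7.8) | out | in |
| Misses only the discharge duplex scan (Protocol 7.7) | out | in |
| Attends the 30-day visit, dies before the 60-day visit | out | in |
| Misses the 30-day visit | out | out (item 5) |
| Time to Hemostasis missing | out | out (item 4) |

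If the first rule governed, the references to missing data in items 3, 4 and 5 would be redundant. This suggests that the list was meant to do the work, but the text does not say so.

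**2. Dependence on outcome**

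- SAP 5.1 gives surgical repair as its example of why Time to Hemostasis may be missing. SAP 2.5.1 item i counts device-attributable vascular injury that needs surgical repair as a Major Complication. Item 4 can therefore remove a subject who failed on both primary endpoints.
- A subject who has a Major Complication and dies before the 30-day visit has no such visit. Item 5 removes that subject although the safety outcome is already known.

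**3. The CTA item**

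The protocol window is "Within 180 days prior to subject informed consent". Item 3 has two readings:

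- More than 12 months beyond the window: 180 + 365 = 545 days before consent.
- A CTA more than 12 months old: 365 days before consent.

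A scan between 365 and 545 days old is a major deviation under the second reading and not under the first.

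**4. Size (illustration)**

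The planned number treated is 263 (Protocol 8.2; SAP section 3). Let m be the share of subjects with at least one missed assessment. The all-assessments rule leaves 263 × (1 − m):

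- m = 5%: 263 × 0.95 = 250
- m = 10%: 263 × 0.90 = 237
- m = 18%: 263 × 0.82 = 216
- m = 30%: 263 × 0.70 = 184

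The values of m are assumptions. The 18% borrows from the EU study in Protocol 1.4, where hemostasis during ambulation was available for 41 of 50 subjects (9/50 = 18% without it). Under the list alone, none of these subjects leaves unless the missed item is the CTA, Time to Hemostasis or the 30-day visit.

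**The case against.** The strongest reply is that nothing decisive rests on this set. That stands: the success rules in SAP 2.4 and 6.3.2 are applied to the PAC and the Safety Evaluation Set, and SAP 4.2 limits the PPS to support. It can also be said that the first sentence of 4.2 states two joint conditions and that the list defines only the second. The grammar allows this, but the exclusion sentence ignores the first condition, the protocol does not contain it, and parts of the list become redundant.

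A reader might infer several stronger points that the documents do not support:

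- **SAP 6.1.2 is a third definition of the set.** It sits among the descriptive summaries, does not mention the PPS, and can be read as applying the list in 4.2. The fair criticism is only that the list is open and the link is unstated.
- **The CTA limit contradicts the 180-day window.** A threshold for a major deviation that is wider than the window is ordinary grading. Known eligibility violations are caught by item 2 whatever the age of the scan. What remains is the ambiguity between the two readings.
- **The undefined Intent-to-Treat dataset leaves the base set in doubt.** SAP 4.2 already says that the PPS is drawn from the PAC.
- **About 21 of 263 would go through deaths** (4/50 = 8% in the EU study; 0.08 × 263 = 21). The EU summary gives no death dates, and deaths before the 30-day visit fall under item 5 as well, so the figure does not separate the two rules.
- **The loss can be computed as 15% to 34%** by treating eight assessments as missed independently at 2% to 5% each. The rates are assumed, and misses cluster because several assessments share a visit.
- **Items 4 and 5 should simply be deleted.** Safety data are not imputed (SAP 5.1). At the planned 5% loss, about 263 × 0.05 = 13 subjects without 30-day follow-up would return and could count as event-free in a crude rate.

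**Conclusion.** The point holds as a defect in the definition of a supportive analysis set. SAP 4.2 contains two rules that classify the same subject differently, the broader rule is absent from the protocol, and the list behind the narrower rule is open. Items 4 and 5 can remove subjects because of a bad outcome, in the direction that favours the device.

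The size is unknown. The range of about 250 down to 184 of 263 rests wholly on assuming that 5% to 30% of subjects miss at least one assessment, and the documents give no expected rate. Neither document says how many subjects items 4 and 5 would remove for outcome reasons.

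The primary tests and the sample size do not depend on this set. The consequence is that agreement or disagreement between the PAC and the PPS, which Protocol 8.1.1 says will be examined, could reflect which sentence was programmed. The point should be corrected before database lock, but it does not threaten the trial's main conclusions.

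**What to change.** In SAP 4.2:

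1. Delete the all-assessments clause and make the list of major deviations closed.
2. State that the ratings in SAP 6.1.2 apply this list and do not add to it. Make any judgement from listings without Time to Hemostasis or complication data.
3. Keep item 5 for the per-protocol safety analysis. State that a subject with an adjudicated Major Complication, or whose Time to Hemostasis is missing because of surgical repair, is not excluded under item 4 or item 5. The missing time is then imputed under the plan's own rule. SAP 5.1 takes the worst value at the same site, whereas Protocol 8.3.3 takes the longest from any subject for surgical repair, so the SAP should name the rule that applies.
4. State whether item 3 means a CTA older than 12 months or one more than 12 months beyond the 180-day window.
5. Note that the protocol's Intent-to-Treat dataset means the PAC. A sentence in the SAP is enough, without a protocol amendment.

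The cost is SAP wording; no new data are needed. The downside is that a few subjects with imputed Time to Hemostasis or incomplete follow-up stay in the supportive set.
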